14.2.2 Model-Based Analysis -- Mixed Effects Model for Repeated Measures (MMRM)

The following key efficacy endpoints and change from the baseline and percent change from baseline will be summarized descriptively for Part A and Part B studies. The change from baseline will be further explored using the MMRM model for Part A or Part B if 5 or more participants are dosed:

[REDACTED]

[REDACTED]

For each item above, a mixed-effects model for repeated measures will be utilized to analyze the change from baseline scores at all post-baseline assessments. The model will include visit as a fixed effect and baseline as a covariate. An unstructured covariance structure will be used to model the variance-covariance matrix of the repeated measurements. If estimation issues arise during the construction of covariance structure, Toeplitz, Autoregressive (1) [AR (1)], or Compound Symmetry (CS) covariance structure will be used, following this sequence until convergence is achieved. If the model still does not converge with the CS structure, no results will be reported. Model-based point estimates ie, least-squares [LS] means are used as the test statistic and will be reported where applicable along with 95% confidence intervals, and p-values.

Line plots of change from baseline scores will be plotted with standard error bars.

Example SAS code that will be used for this model is below:

```
proc mixed data=data1 method=rm;  
class subjid Visit;  
model chg = base Visit / ddfm=kr;  
repeated visit / type=un subject=subjid;  
lsmeans visit / cl;  
run;
```

where chg is the change from baseline in the [redacted] of interest. In all statistical testing, the level of significance will be set at 5%, with no correction for multiple testing.

Additional analysis of variability in remote assessment:

For [redacted] with remote assessments, the mixed-effects model for repeated measures will be repeated with the day of remote assessment instead of the visit. Linear terms will be examined for the day of the visit. Random effects residuals derived from the model indicate the deviation of each individual from their own slope on each day, providing the difference from a statistically expected observation. These residuals will be used to investigate increased variability in response to treatment, plotting the residuals by day of remote assessment.

[redacted]

[redacted]

[redacted]

[redacted]

Note: The start day of IP administration is Day 1, and all sampling times are relative to this time.

[redacted]

[redacted]

[Redacted]

[Redacted]

[Redacted]

Note: The start day of IP administration is Day 1, and all sampling times are relative to this time.

[Redacted]

b To be collected only when participant consent is given.

[Redacted]

[Redacted]

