13.5. Efficacy Analysis

The endpoints for each of the [REDACTED] are change from baseline scores at each postbaseline assessment. Descriptive statistics of scores and change from baseline scores will be summarized based on the Full Analysis Set. These endpoints will also be analyzed using a mixed-effects model for repeated measures. The model will include baseline [REDACTED]

and assessment time point. Model-based point estimates (ie, least squares means, 95% confidence intervals, and p values) at each time point will be reported where applicable. An unstructured covariance structure will be used to model the within-participant errors. If there is a convergence issue with the unstructured covariance model, a Toeplitz or Autoregressive (1) [AR(1)] covariance structure will be used, following this sequence until convergence is achieved. Line plots of change from baseline scores will be plotted with standard error bars. Other continuous efficacy endpoints, including [REDACTED] will be summarized using similar methods.

Additional analyses will be detailed in the SAP.

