10.3 Randomization

This study does not involve any randomization of participants.

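### In a single arm, baseline-adjusted MMRM least-squares means carry standard errors that omit baseline sampling variation, so their 5% tests and 95% intervals are anti-conservative on average

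*SAP*

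**What the plan says.** SAP 14.2.2 fits a repeated-measures model to change from baseline, for Part A or Part B, once 5 or more participants have been dosed. On the model terms it says "The model will include visit as a fixed effect and baseline as a covariate", and the sample code reads "model chg = base Visit / ddfm=kr". On covariance it says "An unstructured covariance structure will be used to model the variance-covariance matrix of the repeated measurements", with Toeplitz, AR(1) and compound symmetry as fallbacks.

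The estimates come from "lsmeans visit / cl". No AT option is given, so the covariate is held at its sample mean. The least-squares means serve as the test statistic and "will be reported where applicable along with 95% confidence intervals, and p-values". On error control: "In all statistical testing, the level of significance will be set at 5%, with no correction for multiple testing".

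Protocol 13.5 also puts baseline and time point in the model and says "Model-based point estimates (ie, least squares means, 95% confidence intervals, and p values) at each time point will be reported where applicable".

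There is one open-label regimen. SAP 10.3 says "This study does not involve any randomization of participants", and SAP 13.1 has the two parts tabulated separately. SAP 13.1 also defines baseline for one redacted group of measures as a 7-day average before Day 1.

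**The concern.** A baseline covariate normally earns its place by sharpening a between-arm contrast, in which the baseline-mean term largely cancels. Here there is no second arm. The covariate removes variance from the residual, and so from the reported standard error, but it does not make the mean change any less variable from one sample to the next. The apparent gain in precision is not real if the target is mean change in the PD-MCI population.

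Kenward-Roger does not repair this. It allows for having estimated the covariance matrix, but the model still treats the observed baselines as fixed constants.

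At stake are the model-based efficacy intervals and p-values that support signal-finding. The error runs towards false signals, and it is separate from the uncorrected multiplicity.

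**Working it through.** **Inputs from the documents.** Model, least-squares-mean request, 5% level and 95% intervals: SAP 14.2.2. Planned completers, 10 in Part A and 20 in Part B: SAP 10.2. Minimum of 5 dosed: SAP 14.2.2.

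**Inputs assumed.** The documents give no SDs and no test-retest correlation, so rho is varied. Equal pre and post SDs, normality and complete data are assumed. The efficacy rows of the visit schedules are not legible. Three post-baseline visits for Part A and six for Part B are taken from SAP Tables 1A and 1B.

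**Step 1: the estimate.** With complete data the least-squares mean at the sample-mean baseline is intercept + b × x̄, which equals the raw mean change at that visit.

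**Step 2: its variance.** Let s²_res be the residual variance, b the slope of change on baseline and s²_base the baseline variance.
- Model variance: s²_res / n
- Sampling variance of the same estimate: (s²_res + b² s²_base) / n

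With equal SDs, b = rho − 1 and R² = (1 − rho)/2. Hence model SE / true SE = f = √((1 + rho)/2).

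**Step 3: the stated 5%.** With baselines held fixed, or with b = 0, f = 1 and the test has its 5% level. For population mean change the single-visit error is 2 × P(t with n − 2 df > t_crit × f). Example, n = 10 and rho 0.7: f = √0.85 = 0.922, t_crit = 2.306, product 2.126, error 6.6%.

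| rho | f | n = 5 | n = 10 | n = 20 |
|---|---|---|---|---|
| 0.9 | 0.975 | 5.3% | 5.5% | 5.6% |
| 0.8 | 0.949 | 5.7% | 6.0% | 6.2% |
| 0.7 | 0.922 | 6.1% | 6.6% | 6.9% |
| 0.5 | 0.866 | 7.0% | 8.1% | 8.6% |
| 0.3 | 0.806 | 8.3% | 10.0% | 10.8% |

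**Step 4: the repeated-measures model.** The SAP model was simulated (REML, unstructured, common slope, true mean change zero) and read at the last visit. SAS was not available, so the Kenward-Roger degrees of freedom were bracketed by n − 2 and n − 1.

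| rho | n = 10, 3 visits | n = 20, 6 visits |
|---|---|---|
| 0.9 | 5.4–5.8% | 5.4–5.5% |
| 0.8 | 5.9–6.3% | 6.1–6.2% |
| 0.7 | 6.6–7.0% | 6.7–6.8% |
| 0.5 | 8.0–8.5% | 8.4–8.5% |

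Without the covariate the same simulation gives 4.7–5.0% (n = 10) and 4.9–5.1% (n = 20).

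**Step 5: endpoints with a 7-day average baseline.** Let r be the single-day reliability, with independent daily errors and an unchanged true score.
- Single post score: R² = (1 − r) / (8(6r + 1)). This is 0.5/32 = 1.6% at r = 0.5 and 0.2/46.4 = 0.4% at r = 0.8. Error is about 5.0–5.2%.
- Post score also a 7-day average: R² = (1 − r) / (12r + 2). This is 0.5/8 = 6.3% and 0.2/11.6 = 1.7%. Error is about 5.2–5.7%.

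**Step 6: interval width.** Dropping the covariate multiplies the mean half-width by (t_{n−1} c_{n−1}) / (t_{n−2} c_{n−2} f), where c is the mean of the sample SD relative to sigma. At n = 10 this is (2.262 × 0.9727)/(2.306 × 0.9693) = 0.984, divided by f: +1% at rho 0.9 and +14% at rho 0.5. At n = 20 it is +2% and +15%. At n = 5 the factor is 0.890, giving −9% at rho 0.9 and +3% at rho 0.5.

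**The case against.** **The test is valid given the observed baselines.** This is correct for a narrower question: mean change at this sample's mean baseline. The SAP does not state an unconditional target in so many words. But nowhere legible does it limit inference to the observed baselines, and it uses these tests for signal-finding. The defence explains the behaviour without making the stated level right for population mean change.

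**Not every interval is too narrow.** A reader might infer that all the model-based intervals are too narrow and all the p-values too small. That does not follow. The covariate costs a degree of freedom and its slope is estimated. In single-visit simulations the adjusted interval was wider than the unadjusted one in 53% of datasets at n = 10, rho 0.8; 24% at n = 20, rho 0.7; and 58 to 73% at n = 5. The claim concerns average coverage.

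**The size rests on unseen inputs.** This stands. Rho and the number of efficacy visits are assumptions, and at rho 0.9 the excess is about half a percentage point. For the 7-day-average group it can be negligible, so the 8% figure must not be applied to all endpoints.

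**The consequence is limited.** This also stands. The efficacy modelling is exploratory, no legible decision rule hangs on p < 0.05, and unadjusted change is summarised descriptively with n, mean and SD. That bears on severity; it does not make the reported p-values and intervals correct.

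**Conclusion.** The concern holds in a limited form. As coded, the single-arm model tests the mean change with a standard error that omits baseline sampling variance. For population mean change, the intervals under-cover on average and the 5% level is exceeded whenever change correlates with baseline. Under the stated assumptions the excess at n = 10 to 20 runs from about half a point (rho 0.9) to about 3.5 points (rho 0.5). It nearly vanishes where a 7-day average baseline is set against a single post score.

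A reader might go further and conclude that the trial's main result is compromised. The documents do not support that: the primary endpoint is TEAE incidence, which this model does not touch. The change should be made, but it is not critical.

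**What to change.** Either of two changes restores the intended inference:

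- **Drop the covariate.** Fit chg = Visit with ddfm=kr and unstructured covariance. This is one line of code. With complete data the point estimates do not move. The cost is that baseline no longer informs the estimates when visits are missing.
- **Model baseline as a response.** Make the baseline score the first level of Visit under an unstructured matrix and estimate each post-minus-baseline contrast. This keeps baseline's use for missing data. The cost is more covariance parameters: with six post-baseline visits, from 6 × 7/2 = 21 to 7 × 8/2 = 28, on about 20 participants, so the covariance fallback becomes more likely.

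Report the intervals and p-values from the chosen model. Record the departure in SAP 6.1, because Protocol 13.5 also includes baseline. Expect the mean half-width to change by about +1% to +15% at n = 10 to 20; it may narrow at n = 5.

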16.0 Safety and Tolerability Analyses

All safety analyses will be performed using the safety analysis set. The baseline for safety data is defined as the last non-missing value prior to the first dose of the investigational product.

Safety and tolerability of SAGE-718 will be evaluated by treatment-emergent adverse events (TEAEs) and change from baseline vital signs, clinical laboratory analytes, electrocardiograms (ECGs), safety electroencephalogram (EEG), and responses on the Columbia–Suicide Severity Rating Scale (C-SSRS). Safety data will be listed by the participant and summarized using descriptive statistics (mean, median, range, percentages).

16.1 Adverse Events

TEAEs are defined as any AEs with an onset date on or after the date of the first dose of IP or any worsening of a preexisting medical condition/AE with onset after the start of IP and throughout the study. An AE leading to treatment discontinuation is defined as an AE with action taken of investigational product as Drug Withdrawn. AEs will be coded using the Medical Dictionary for Regulatory Activities MedDRA version 23.0u.

An overall summary of TEAEs, including the number of events, reported, the number and percentage of participants reporting at least one TEAE, the number and percentage of participants reporting at least one related TEAE, the number and percentage of participants by maximum severity, the number and percentage of participants discontinuing due to an adverse event, the number and percentage of participants with at least one serious adverse event, and the number and percentage of deaths will be presented.

A breakdown of the number and percentage of participants reporting each adverse event, categorized by System Organ Class (SOC) and preferred term (PT), will be presented. Note that counting will be by participant, not event, and participants are only counted once within each SOC and PT.

A further tabulation of these data, categorized by relationship (to SAGE-718), will be presented. Participants with multiple events within a particular body system or preferred term will be counted under the category of their drug-related event (related and not related) within SOC and PT. Relationship to SAGE-718 is categorized as related or not related.

A summary of events reported, categorized by severity, will also be provided. Participants with multiple events within a particular SOC and PT will be counted under the category of their most severe event in the following order: severe > moderate > mild within that SOC and PT.

A summary of adverse events leading to discontinuation of SAGE-718 will be provided, grouped by body system and preferred term.

All adverse events (including non-treatment-emergent events) recorded on the CRF will be listed.

Handling of missing AE start dates is defined in Appendix 3. Missing data for severity or relatedness to treatment will not be imputed.

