The Screening Period begins with the informed consent process for prospective participants, including study partners. Subsequent screening assessments will be performed between Day -21 and

Day -8 to determine eligibility, including assessments of [REDACTED].

Baseline Period

The Baseline Period will occur from Day -7 through Day -1. During this period, each participant will receive dietary counseling to aid in choosing a morning meal containing approximately 30 g fat to consume prior to dosing. On Day -7 (± 1 day), participants will visit the clinic for confirmation of continued eligibility and collection of baseline [REDACTED] and safety data. Additionally, participants will be trained on the use of a mobile data capture device to perform daily [REDACTED]. Participants will continue to complete daily assessments of [REDACTED] using the mobile device at home during the Baseline Period. On Day -1, participants will return to the study site for confirmation of continued eligibility and collection of baseline [REDACTED] and safety data.

Treatment Period

Beginning on Day 1 and continuing through Day 14 in Part A and Day 28 in Part B, participants will self-administer 3.0 mg SAGE-718 (as six 0.5-mg oral tablets), once per day in the morning within 1 hour after initiating a meal containing approximately 30 g of fat, in accordance with the guidelines provided in a nutritional information brochure. Participants will continue to complete daily assessments of [REDACTED] via mobile device either remotely (at home), or in the clinic at scheduled visits and will track IP dosing and predose food intake in a participant diary.

At scheduled visits during the Treatment Period, participants will arrive at the clinic in the morning prior to IP dosing and completion of daily mobile device tasks. Following predose procedures, participants will eat a morning meal, then take the IP and complete the mobile device tasks under staff supervision.

At scheduled clinic visits during the Treatment Period, safety, efficacy, and [REDACTED] will be performed, and study staff will dispense a sufficient amount of SAGE-718 for daily administration until the next scheduled study visit. In addition to weekly clinic visits, study staff will contact participants by telephone on Day 4 to document any TEAEs and/or changes in concomitant medications.

Follow-up Period

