12.2. Adverse Events and Serious Adverse Events

12.2.1. Adverse Event Definition

An AE is any untoward medical occurrence in a patient or clinical investigation participant administered a pharmaceutical product and that does not necessarily have a causal relationship with this treatment. An AE can therefore be any unfavorable and unintended sign (including an abnormal laboratory finding), symptom or disease temporally associated with the use of a medicinal (investigational) product whether or not related to the medicinal (investigational) product. In clinical studies, an AE can include an undesirable medical condition occurring at any time, including baseline or washout periods, even if no study treatment has been administered.

A TEAE is defined as an AE with onset after the start of IP, or any worsening of a preexisting medical condition/AE with onset after the start of IP and throughout the study. The term IP includes any Sage IP, a comparator, or a placebo administered in a clinical study.

Laboratory abnormalities and changes from baseline in vital signs, and ECGs are considered AEs if they result in discontinuation or interruption of study treatment, require therapeutic medical intervention, meet protocol specific criteria (if applicable) or if the investigator considers them to be clinically significant. Any abnormalities that meet the criteria for a SAE should be reported in an expedited manner. Laboratory abnormalities and changes from baseline in vital signs and ECGs that are clearly attributable to another AE do not require discrete reporting (eg, electrolyte disturbances in the context of dehydration, chemistry, and hematologic disturbances in the context of sepsis).

All AEs that occur after any participant has signed the informed consent form (ICF) and throughout the duration of the study, whether or not they are related to the study, must be reported to Sage Therapeutics.

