13.6.1. Adverse Events

AEs will be coded using Medical Dictionary for Regulatory Activities version 22.0 or higher. A TEAE is defined as an AE with onset after the first dose of IP. The analysis of AEs will be based on the concept of TEAEs. The incidence of TEAEs will be summarized by System Organ Class and preferred term. In addition, summaries will be provided by intensity (mild, moderate, severe) and by causality (related, not related) to IP.

Any TEAEs leading to discontinuation or interruption of treatment or withdrawal from the study and any treatment-emergent SAEs will be summarized.

All AEs and SAEs (including those with onset or worsening before the start of IP) through the end of the study will be listed.

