6.1 Changes from the Protocol

Protocol section 13.6.6 mentions that the prior and concomitant medications will only be listed. Along with the listing, a summary table will also be provided.

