9.0 Study Endpoints

9.1 Primary Endpoint

- Incidence of treatment-emergent adverse events (TEAEs)

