13.0 Statistical Methods

13.1 General Statistical Methodology

All analyses will use SAS version 9.4 or higher.

Unless otherwise noted, continuous variables will be summarized using the number of observations (n), mean, standard deviation (std), median, first quartile (Q1), third quartile (Q3), minimum, and maximum values. The minimum and maximum values will be displayed to the same level of precision as the raw data; the mean, median, Q1, and Q3 values to one additional decimal place and the std to two additional decimal places.

Categorical variables will be summarized using counts and percentages. Percentages will be rounded to one decimal place, except 100% will be displayed without any decimal places, and percentages will not be displayed for zero counts.

Any data points that are not within the expected range due to subjects not following task instructions to complete the tasks will be flagged as invalid by CANTAB EDC. These data points will be excluded from the analyses and reports.

All participants will be used in the analyses as per the analysis populations, using all non-missing data available. No imputation process will be used to estimate missing data.

For all safety, efficacy, and other analyses, where applicable, the baseline is defined as the last assessment prior to the first dose of study IP.

All summary tables will be reported separately for Part A and Part B studies.

For [REDACTED], the baseline is defined as the average assessments over 7 days immediately preceding Day 1.

Prior and concomitant medication start/stop date imputation and adverse event start/stop date imputation are described in Appendix 2 and Appendix 3, respectively.

AEs will be coded using Medical Dictionary for Regulatory Activities (MedDRA) version 23.0u. All TEAEs are defined as an AE with onset after the first dose of IP or any worsening of a preexisting medical condition/AE with onset after the start of IP and throughout the study.

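### SAP 16.1 counts a non-worsening adverse event with a recorded predose onset on Day 1 as treatment-emergent; SAP 13.1 and the protocol do not, and SAP 6.1 does not declare the difference

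*SAP*

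**What the plan says.** Four places define a treatment-emergent adverse event.

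- SAP 16.1, the adverse event section: "TEAEs are defined as any AEs with an onset date on or after the date of the first dose of IP". Worsening of a preexisting condition or event after the start of IP also counts.
- SAP 13.1, the general methods section: "All TEAEs are defined as an AE with onset after the first dose of IP", with the same worsening limb.
- Protocol 12.2.1: "A TEAE is defined as an AE with onset after the start of IP", again with the worsening limb.
- Protocol 13.6.1: "A TEAE is defined as an AE with onset after the first dose of IP", with no worsening limb.

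SAP 6.1, which records changes from the protocol, has one entry. It concerns medications ("Protocol section 13.6.6 mentions that the prior and concomitant medications will only be listed") and adds a summary table. TEAEs are not mentioned there.

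TEAE incidence is the only primary endpoint (SAP 9.1, Protocol 6.2.1).

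**The concern.** SAP 16.1 tests a calendar date and includes the whole of Day 1. The other three definitions test whether onset came after dosing. The two kinds of rule can differ only on the day of the first dose, and the protocol leaves room for an event in that gap:

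- Reporting starts at consent: "All AEs that occur after any participant has signed the informed consent form (ICF) and throughout the duration of the study" must be reported (Protocol 12.2.1).
- Dosing is not the first thing that happens at a treatment visit: "Following predose procedures, participants will eat a morning meal, then take the IP" (Protocol Synopsis, Treatment Period).
- Vital signs are scheduled on Day 1 in both parts (Protocol Tables 2 and 4). They include standing measurements (Protocol 12.1.4), and a change that the investigator judges clinically significant is an adverse event (Protocol 12.2.1).

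The date rule also sits awkwardly with the safety baseline, which is the last value before the first dose (SAP 16.0). A predose Day 1 reading could serve as the baseline value while the event it prompted is labelled treatment-emergent.

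At stake is the membership of the primary endpoint. One flag would also feed every planned adverse event table: Tables 14.3.1.1 to 14.3.1.8, each for Parts A and B, so 8 × 2 = 16 tables, all titled treatment-emergent.

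**Working it through.** **Inputs.** The four definitions above. Planned numbers dosed are 11 in Part A and 22 in Part B (Protocol 7.2, SAP 10.1). The parts are tabulated separately (SAP 13.1). The documents give no expected TEAE incidence and no count of Day 1 events.

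**The plan's own figure.** The only sample-size figure is about 33 dosed for 30 completers at 10% dropout. 30/(1 − 0.10) = 33.3 and 30 × 1.10 = 33, so it reproduces, and 11 + 22 = 33. The point does not depend on it.

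**Step 1: classify test onsets by the onset limb alone.** The rule in SAP 16.1 is date(onset) ≥ date(first dose). The rule in SAP 13.1 and the protocol is onset > first dose.

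| Onset | SAP 16.1 | SAP 13.1 and protocol |
|---|---|---|
| Day −1 | no | no |
| Day 1, before dosing | **yes** | **no** |
| Day 1, after dosing | yes | yes |
| Day 2 | yes | yes |

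Only the predose Day 1 onset changes class.

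**Step 2: apply the worsening limb.** A predose Day 1 event that worsens after dosing is a TEAE under SAP 13.1, SAP 16.1 and Protocol 12.2.1 alike. Protocol 13.6.1 omits that limb, but 12.2.1 supplies it. The events on which SAP 16.1 differs from both 13.1 and the protocol are therefore those with a recorded predose Day 1 onset and no later worsening.

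**Step 3: direction.** Any onset after the first dose also falls on or after the first-dose date, and the worsening limb is the same in both SAP sections. The 16.1 set contains the 13.1 set, so incidence under 16.1 minus incidence under 13.1 is zero or positive.

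**Step 4: step per participant.** If such an event is a participant's only TEAE, incidence moves by

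- Part A: 1/11 = 0.0909, or 9.1 percentage points
- Part B: 1/22 = 0.0455, or 4.5 percentage points

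These are the steps for reclassifying any one participant for any reason. They say nothing about how often it would happen.

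**The case against.** The best defence is that SAP 16.1 is the operational form of the general statement in 13.1. It is the dedicated adverse event section and specifies the tables. Its date rule also works with Appendix D, which handles only day, month and year. A programmer would most naturally follow it, so two competing primary results are unlikely. On-or-after-date is also a cautious rule when onset time is unknown.

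Much of that stands, and it lowers the severity. It does not remove the point. SAP 16.1 is not limited to events of unknown time, Protocol 12.2.4 has the investigator report onset time as well as date, and following 16.1 counts recorded predose events that the protocol excludes without SAP 6.1 saying so.

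The Day 1 predose activity should not be overstated either. The procedure order in the notes to Protocol Tables 2 and 4 applies to procedures scheduled at the same time point. The visible schedules show no Day 1 clinical laboratory tests in either part and no Day 1 ECG in Part B.

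A reader might also infer that events whose start date Appendix D imputes to the first-dose date would be lost under 13.1. The documents do not support that. It requires programming 13.1 as a strict date comparison, which would also drop genuine postdose Day 1 events, contrary to 13.1's own words. SAP 13.1 itself invokes the imputation, and moving an ambiguous start to the first-dose date fits with treating the event as treatment-emergent. On these cases 13.1 is less explicit than 16.1; it does not plan a different result.

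**Conclusion.** The inconsistency is real and minor. The sole primary endpoint has two definitions in the SAP. They differ for one narrow class: events with a recorded predose onset on Day 1 that do not worsen after dosing.

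The number of such events cannot be derived from the documents. Exposure is the predose part of one calendar day per participant, so it is probably small. The error can only be an over-count, the documents state no test or threshold for TEAE incidence, and SAP 16.1 lists all adverse events, including those that are not treatment-emergent, so a reclassification could be traced.

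Two stronger readings should be avoided. One is that every predose Day 1 event is affected; the worsening limb rules that out. The other is that the plan carries a bias of 9.1 or 4.5 points. Those figures assume the planned 11 and 22 are dosed and that the event is a participant's only TEAE, and they are steps per participant rather than expected effects.

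**What to change.** Put one definition in SAP 13.1 and 16.1 and keep the worsening limb. Then:

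1. Where adverse event onset time and first-dose time are both in the analysis database, do not count an event whose recorded onset precedes the first dose unless it worsens after dosing.
2. Count as treatment-emergent any event on the first-dose date with no onset time, and any event whose start date is imputed to that date. SAP 16.1 already gives this result; state it in both sections.
3. If either time is not in the database, use the on-or-after-date rule in both sections and declare it in SAP 6.1 as a departure from the protocol.

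The cost is one harmonised sentence in two sections, a small derivation and, if step 3 applies, a line in SAP 6.1. One check comes first. The protocol has the investigator report onset time (12.2.4) and has dosing time noted in source documents (9.4), but whether both reach the database depends on the two CRFs named in SAP 6.0. These were not among the documents available here. If the database is already locked, SAP 6.0 provides for describing and justifying the change in the clinical study report.
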